#### 12.1.3 Descriptive Statistics

All data will be presented in listings, ordered by sequence and subject, unless otherwise specified.

Descriptive statistics for continuous variables (number of subjects [n], number and percentage of subjects with missing data, mean, standard deviation, median, first and third quartiles, minimum and maximum for continuous data, and the n and absolute and relative [%] frequency for categorical data) will be presented by exposure and overall at each time point, where applicable.

Descriptive statistics for PK parameters will also include the geometric mean and coefficient of variation.

Confidentiality Statement: Data and information contained in this document are considered to constitute trade secrets and confidential commercial information, and the legal protections provided to such trade secrets and confidential information are hereby claimed under the applicable provisions of applicable law. No part of this document may be publicly disclosed without the written consent of Philip Morris Products SA.

Baseline, admission and screening data (i.e., anything prior to product exposure) will be summarized by sequence and overall where appropriate.

#### 12.1.4 Handling of Missing Values and of Values outside the Detection Limits

In general, missing data will not be imputed in this study, due to the nature of the measurements and the short periods of exposure and use. However, for questionnaire data total scores and domain or subscale scores may use a certain degree of imputation by averaging across individual item scores. Further details will be provided in the SAP.

Values below the lower limit of quantification (LLOQ) will be imputed using  $0.5 \times$  lower limit of quantification. For values above the upper limit of quantification (ULOQ), i.e., preceded by a “>”, for example “>xx”, the numerical xx will be used for calculation and reporting in summary tables. The number of values below LLOQ or above ULOQ will be presented in each summary table.

#### 12.1.5 Significance Level for Inferential Analysis

For all endpoints, unless otherwise stated, statistical tests will be two-sided and conducted at the 5% significance level and all quoted confidence intervals (CIs) will be two-sided 95% CIs.

No formal adjustment of the test-wise alpha level for multiple testing is necessary, as no claim will be made based on the outcome of the individual tests.

### 12.2 Determination of Sample Size and Power Consideration

A total of 62smokers will be randomized. This is calculated by adding up sample sizes separately estimated for each analysis.

A total of 44 subjects are needed to estimate the mean  $C_{max}$  parameter ratio between THS 2.2 and CC with a 90% probability of obtaining a margin of error (95% CI) of at most  $\pm 20\%$ , assuming that THS 2.2 have a nicotine PK profile similar to CC ( $C_{max}$  ratio equal to 1.00) and a 10% dropout rate.

A total of 18 subjects are needed to estimate the mean  $C_{max}$  parameter ratio between THS 2.2 and NNS with a precision allowing for the lower bound of the 95% CI exceeding 1.00, with 90% power and assuming a 10% dropout rate. The anticipated geometrical  $C_{max}$  ratio between THS 2.2 and NNS is 1.55, based on data reported by [Gourlay and Benowitz, 1997](#), and [Johansson et al, 1991](#).

Confidentiality Statement: Data and information contained in this document are considered to constitute trade secrets and confidential commercial information, and the legal protections provided to such trade secrets and confidential information are hereby claimed under the applicable provisions of applicable law. No part of this document may be publicly disclosed without the written consent of Philip Morris Products SA.

The estimates for the within-subject CV for nicotine  $C_{max}$  (36%) and  $AUC_{(0\text{-last})}$  (21%) are based on the data collected in the ZRHX-PK-02 clinical study (PMI, 2012a) comparing the nicotine PK profiles of THS 2.1, the predecessor of THS 2.2 and CC. In the absence of data comparing THS and NNS, the same CVs were assumed for the calculation of the sample size related to the THS 2.2:NNS comparison.

Sample size calculations were conducted using SAS version 9.2 for the 95% CI of the mean differences between paired observations (proc power onesamplemeans) in the natural log scale (Senn, 2002). The SAS implementation of the method published by Beal, 1989 was adopted to estimate the probability of obtaining at most the target confidence interval of  $\pm 20\%$ .

## 12.3 Analysis Populations

All analyses will be based on actual product exposure. All endpoints (other than safety) will be analysed using the PK Analysis sets. Safety will be analysed using the safety population.

### 12.3.1 PK Populations

The analysis populations for the PK endpoints are composed of two analysis sets to allow the comparison between THS 2.2 and NNS separately from the comparison between THS 2.2 and CC.

The PK populations consist of all the randomized subjects who give informed consent, completed at least one of the single use Day 1 or Day 3, and for whom at least one PK parameter can be derived. Only subjects without major protocol deviations (to be defined in the SAP) will be included in the PK analysis sets.

### 12.3.2 Safety Population

The safety population consists of all the subjects who give informed consent and have at least one exposure to THS 2.2 (including the product test at Admission Day).

## 12.4 Demographics and Baseline Characteristics

Demographic and other baseline characteristics will be reported for the PK and safety populations. Appropriate summary statistics will be provided as described in Section 12.1.3.

Confidentiality Statement: Data and information contained in this document are considered to constitute trade secrets and confidential commercial information, and the legal protections provided to such trade secrets and confidential information are hereby claimed under the applicable provisions of applicable law. No part of this document may be publicly disclosed without the written consent of Philip Morris Products SA.

## 12.5 Primary Endpoints

### 12.5.1 Primary Endpoint Analysis Variables

Nicotine PK parameters will be derived from plasma nicotine versus time data using a non-compartmental technique. In particular:

$C_{\max}$	Maximum observed plasma concentration. $C_{\max}$ will be reported as long as there is at least one quantifiable concentration post-exposure
$AUC_{(0-\text{last})}$	Area under the plasma concentration-time curve from start of product use to the time of the last quantifiable concentration (linear trapezoidal method).

### 12.5.2 Baseline Comparability

Not applicable.

### 12.5.3 Descriptive Analysis

Primary endpoints will be summarized as described in [Section 12.1.3](#).

An analysis of variance (ANOVA) will be conducted on  $AUC_{(0-\text{last})}$  and  $C_{\max}$  endpoints in the natural logarithmic scale. The model will include terms for sequence, subjects within sequence, period and product exposure as fixed effect factors. The results of this analysis for each of  $AUC_{(0-\text{last})}$  and  $C_{\max}$  are presented in terms of adjusted geometric least square means and 95% CIs for the THS 2.2:CC and THS 2.2:NNS ratios.

This approach is consistent with the guidelines in the European Medicines Agency's guidelines for bioequivalence investigations ([EMA, 2008](#)) and FDA's Center for Drug Evaluation and Research ([FDA, 2001](#)). Carry-over effect will not be tested, as it cannot be statistically distinguished from the interaction between treatment and period in a 2x2 crossover design ([ICH E9, 1998](#)).

A sensitivity analysis will be conducted should there be 20% or more missing PK parameter values, by repeating the above analyses using mixed effects ANOVA model in the natural log scale, with a restricted maximum likelihood method to estimate mean differences and variances as suggested by FDA ([FDA, 2001](#)). Subjects within sequence will be used as random effects and fixed effects are period, sequence, and product exposure. To evaluate the sensitivity to the distributional assumptions, point and interval estimates will also be

Confidentiality Statement: Data and information contained in this document are considered to constitute trade secrets and confidential commercial information, and the legal protections provided to such trade secrets and confidential information are hereby claimed under the applicable provisions of applicable law. No part of this document may be publicly disclosed without the written consent of Philip Morris Products SA.

estimated by means of the percentile bootstrap technique, using 2000 bootstrap samples which preserve the number of subjects per sequence.

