The sample size of this study is based on our current understanding of THS 2.1, the previous prototype of THS 2.2, where the within-subject coefficient of variation for nicotine  $C_{max}$  and  $AUC_{(0\text{-last})}$  was found to be approximately equal to 36% and 21%, respectively.

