### **6.3 Method for Assigning Subjects to Study Arms**

Randomization to product exposure sequence will be done through an Interactive Telephone and Web Response System.

Each sex and each of the smoking level (ISO nicotine levels  $\leq 0.6$  mg and  $> 0.6$  to  $\leq 1$  mg) will have a quota applied to ensure they represent at least 40% of the total study population allocated within each of the following analysis groups:

- Group-1: composed of sequences 1 and 2.
- Group-2: composed of sequences 3 and 4.

In particular, the maximum number of subjects having the same sex or nicotine level value will be limited to 26 in Group-1 and 10 in Group-2.

The randomization of the planned sample size of 62 subjects will be ensured by applying quota to the number of subjects per each sequence (22 subjects for sequences in Group-1, and 9 subjects for sequences in Group-2).

Subjects will be randomly assigned to one of the four product exposure sequences by means of a permuted-block schema. Block size and other randomization details will be available in the randomization plan.

The randomization plan will be generated by an independent statistician and none of the sponsor staff, investigators or study subjects will have access to the randomization schema prior to randomization.

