where  $X_{THS}$  and  $X_{NNS}$  are the median values of the THS 2.2 and NNS, respectively.  $t_{max}$  will be analysed on the original scale using the Wilcoxon Signed-Rank Test with a type I error  $\alpha = 0.025$  (one-sided test), as values are ordinal/discrete, and the assumption of normality may be questionable.

- To determine if the rate and the amount of nicotine absorbed of the THS 2.2 is higher relative to NNS the following hypothesis will be tested for both  $C_{max}$  and  $AUC_{(0-last)}$  parameters:

$$H_0: X_{THS}/X_{NNS} = 1.0 \quad H_A: X_{THS}/X_{NNS} > 1.0$$

where  $X_{THS}$  and  $X_{NNS}$  are the adjusted geometrical means of THS 2.2 and NNS, respectively.  $H_0$  is rejected with a type I error  $\alpha = 0.025$  (one-sided test), if the lower bound of the 95% CI for the  $X_{THS}/X_{NNS}$  ratio is higher than 1.0.

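### The supportive percentile bootstrap in section 12.5.3 covers less than its nominal 95% and is narrower than the ANOVA interval even with exactly log-normal data, mildly in Group-1 and clearly in Group-2

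*Protocol*

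**What the plan says.** Section 12.5.3 makes a fixed-effects ANOVA on the log scale the main analysis of Cmax and AUC(0-last). It then adds a bootstrap and states its purpose: "To evaluate the sensitivity to the distributional assumptions, point and interval estimates will also be" "estimated by means of the percentile bootstrap technique, using 2000 bootstrap samples which preserve the number of subjects per sequence". The interval type, the number of resamples and the resampling scheme are thus fixed in the protocol. No small-sample correction is named.

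The bootstrap sentence stands in a paragraph that opens with "A sensitivity analysis will be conducted should there be 20% or more missing PK parameter values". The text does not make clear whether the bootstrap is tied to that trigger or always runs.

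Section 12.1.5 sets the level: "all quoted confidence intervals (CIs) will be two-sided 95% CIs". Section 6.3 sets the sequence sizes: "22 subjects for sequences in Group-1, and 9 subjects for sequences in Group-2". For THS 2.2 against NNS, section 12.6.3 rejects the null hypothesis "if the lower bound of the 95% CI for the" ratio of adjusted geometric means lies above 1.0.

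**The concern.** Resampling k subjects within a sequence has two known small-sample faults. The bootstrap variance of each sequence mean uses the divisor k instead of k − 1, so it is too small by the factor (k − 1)/k. Raw percentiles then behave like normal quantiles, whereas the ANOVA uses t quantiles on 2k − 2 degrees of freedom. Both faults shorten the interval whatever the distribution of the data.

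The check is meant to show whether the log-normal assumption matters. Anyone who compares the widths of the two intervals will see mostly the small-sample shortfall. A sensitivity analysis should be able to weaken the main result, but on precision this one will nearly always look more favourable than the ANOVA, under a 95% label that it does not earn.

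**Working it through.** **Inputs.**
- Sequence sizes are 22 and 9 (section 6.3). The sample sizes were set "with 90% power and assuming a 10% dropout rate" for NNS, with the same dropout rate for CC (section 12.2). 44 × 0.9 = 39.6 and 18 × 0.9 = 16.2, so about 20 and 8 per sequence remain.
- The within-subject CV for Cmax and AUC(0-last) "was found to be approximately equal to 36% and 21%, respectively" (Synopsis, and section 12.2). For Cmax the SD of the paired log difference is √(2·ln(1 + 0.36²)) = 0.494.
- The precision target of ±20% is read as ln 1.2 = 0.182 on the log scale.

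**The plan's own figures.** The method of section 12.2 (probability of at least 90% that t·S/√n ≤ 0.182, with SD 0.494) gives n = 40, and 40 × 1.1 = 44 as stated (40/0.9 would give 45). For NNS, a ratio of 1.55 at one-sided 0.025 gives n = 16 (power 91.2%), and 16/0.9 = 17.8, so 18 as stated. The inputs are therefore read as the sponsor read them.

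**Formulas, for normal log differences and k per sequence.**
- Width relative to the ANOVA interval ≈ √((k − 1)/k) × 1.96 / t(0.975; 2k − 2).
- Coverage ≈ P(|T| < 1.96·√((k − 1)/k)), with T on 2k − 2 degrees of freedom.

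The CV cancels, so the result applies to Cmax and AUC(0-last) alike.

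For k = 8: √(7/8) = 0.935; 0.935 × 1.96 = 1.833; t(14) = 2.145; ratio 0.855; coverage 91.2%.

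For k = 20: √(19/20) = 0.975; 0.975 × 1.96 = 1.910; t(38) = 2.024; ratio 0.944; coverage 93.6%.

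**Simulation** of the planned procedure (2×2 crossover log ratio, 2000 resamples within sequence, 8,000 to 18,000 trials per setting):

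| k per sequence | Coverage, formula | Coverage, simulated | Mean width ratio, simulated |
|---|---|---|---|
| 22 (Group-1, full) | 93.8% | 93.4% | 0.946 |
| 20 (Group-1, 10% dropout) | 93.6% | 93.6% | 0.941 |
| 9 (Group-2, full) | 91.7% | 91.5% | 0.868 |
| 8 (Group-2, 10% dropout) | 91.2% | 90.9% | 0.850 |

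The ANOVA t interval covered 94.4 to 95.2% in these runs. A separate simulation with 1000 resamples gave 93.3%, 92.9%, 91.0% and 90.5% in the same order. If the bootstrap runs only with 20% missing values (about 17 and 7 per sequence), simulated coverage is 93.0% and 89.5%.

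**How often it is narrower.** The bootstrap interval was narrower than the ANOVA interval in 99.5 to 99.8% of trials at 20 to 22 per sequence, and in every trial at 8 and 9.

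**What the width can show.** At 20 per sequence the mean width ratio is 0.941 for normal, 0.941 for t3 and 0.938 for skewed differences. It hardly responds to the distribution. The ratio of upper to lower arm does respond: median 1.00 for normal, 1.12 for exponential and 1.18 for lognormal differences. The non-normal cases are assumptions, because the protocol gives no distributional data.

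**Effect on apparent precision.** At 20 per sequence and CV 36%, the half-width is within 0.182 in 97.3% of trials by bootstrap and 91.4% by ANOVA. In 5.9% of trials only the bootstrap interval meets the target.

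**The case against.** The strongest reply is that the bootstrap decides nothing. The Synopsis and section 12.5.3 present the 95% intervals as output of the ANOVA. Section 12.6.3 defines the NNS test on adjusted geometric means, which are also ANOVA output. Section 12.5.4 says that no hypothesis is tested for the primary comparison, and section 12.1.5 disclaims any claim from individual tests. This stands.

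A reader might infer that the lower-bound error for THS 2.2:NNS rises from 2.5% to about 4.4% at 8 per sequence ((100 − 91.2)/2). That is the error of the bootstrap limit, not of the planned test. A reader might likewise infer that a failed ±20% criterion could be turned into a pass. The 5.9% of discordant trials shows how far the two intervals can disagree, but nothing in the protocol lets the bootstrap replace the ANOVA interval. Section 3.3 does not name the interval, however, so a clarifying sentence is worthwhile.

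It would also go too far to say that the bootstrap cannot test distributional assumptions or that it is always narrower. Section 12.5.3 asks for point and interval estimates, asymmetric limits do reveal skewness, and in up to 0.5% of Group-1 trials the bootstrap interval was not narrower.

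Finally, the percentile interval is a common choice, and its shortfall in Group-1, the primary comparison, is only about 1.5 to 2 points. That is why the point is minor. It does not make the 95% label correct in Group-2.

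**Conclusion.** The point holds for the supportive interval only. With exactly log-normal data the planned percentile bootstrap covers about 90 to 92% in Group-2 and about 93 to 93.5% in Group-1. It is about 13 to 15% and 5 to 6% narrower than the ANOVA interval respectively, in practically every trial. A narrower bootstrap interval must not be reported as robustness or better precision. The primary result and the THS 2.2:NNS test are unaffected.

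The figures assume normal log differences with equal variance in the two sequences, equal sequence sizes, and 0 to 10% dropout. If the bootstrap depends on the 20% missing-data trigger, coverage is somewhat lower and the analysis may never run. Severity is minor, and the point matters mainly for Group-2.

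**What to change.** In section 12.5.3, replace the percentile interval by a studentised (bootstrap-t) interval. Keep the 2000 resamples within sequence, compute the crossover ANOVA standard error in each resample, and apply the resulting quantiles to the observed estimate and standard error. Simulated coverage of this interval is about 94 to 95% at 8, 9, 20 and 22 per sequence; a separate run at 8, 9 and 20 gave 94.9 to 95.8%.

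Add one sentence that the ±20% precision criterion and the comparison of the lower bound with 1.00 are judged on the ANOVA interval only. In the same edit, say whether the bootstrap always runs or only under the missing-data trigger.

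The cost is two or three sentences and a few lines of code, with no change to design, sample size or conduct. The downside is that the reported sensitivity interval becomes wider.

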#### 12.5.4 Confirmatory Analyses

Given that the objective of this study is to determine the point estimate and precision of the ratio of THS 2.2:CC for  $C_{max}$  and  $AUC_{(0-last)}$ , there is no statistical hypothesis to be tested.

### 12.6 Secondary Endpoints

#### 12.6.1 Secondary Endpoint Analysis Variables

Nicotine PK parameters will be derived as follows:

$t_{max}$  Time of maximum observed plasma concentration.  $t_{max}$  will be reported as long as there is at least one quantifiable concentration post-exposure

$AUC_{(0-t)}$  Area under the plasma concentration-time curve from zero to the subject-specific time to maximum nicotine concentration following single use of CC or NNS(linear trapezoidal method)

$AUC_{(0-\infty)}$  Area under the plasma concentration-time curve from start of product use extrapolated to infinite time, according to:

$$AUC_{0-\infty} = AUC_{0-last} + \left( \frac{C_{last}}{\lambda_z} \right)$$

Where  $C_{last}$  is the last quantifiable concentration and  $\lambda_z$  is the terminal elimination rate constant

$\lambda_z$  Terminal elimination rate constant, estimated by linear regression analysis of the natural log-transformed concentration-time data

$t_{1/2}$  Terminal elimination half-life, derived as  $\ln(2)/\lambda_z$

More details on PK parameter derivations will be provided in the SAP.

Subjective effects of using THS 2.2 as compared to the CC and to the NNS will be evaluated by analysing domain scores of QSU-brief and MCEQ. Full details of questionnaire domain scores derivation will be provided in the SAP.

Confidentiality Statement: Data and information contained in this document are considered to constitute trade secrets and confidential commercial information, and the legal protections provided to such trade secrets and confidential information are hereby claimed under the applicable provisions of applicable law. No part of this document may be publicly disclosed without the written consent of Philip Morris Products SA.

## 12.6.2 Baseline Comparability

Not applicable.

## 12.6.3 Descriptive Analysis

In general, secondary endpoints will be summarized using the approach described in [Section 12.1.3](#).

The following analyses will be conducted in both Group-1 and Group-2 PK analysis sets:

- AUC(0-∞), AUC(0-t), and t1/2 will be analysed using the same approach adopted for the primary endpoints. No statistical analysis will be performed on the elimination rate constant λz. Data will be summarized and presented together with 95% CI.
- Hodges-Lehmann 95% CI estimates for the median tmax differences will be presented ([Lingling, 2008](#)).
- The use of random effects model is suggested in the context of the analysis of subjective effects of smoking ([Shiffman et al, 2004](#)). Mixed effects ANOVA with the same model terms as planned for the sensitivity analysis of the primary endpoints will be adopted for the analysis of QSU-brief, including all of the different assessment time points as repeated measurements. The analysis will not be adjusted for the assessment prior to T0 ([Fleiss et al, 1985](#)).
- Levels of exhaled CO and of blood COHb will be summarized by means of descriptive statistics reported by exposure. Analysis of COHb levels will be conducted using a mixed model for repeated measures, the same approach as for the QSU-brief.

The following analyses will be conducted only in Group-1 PK analysis set:

- Mixed effects ANOVA with the same model terms as planned for the sensitivity analysis of the primary endpoints will be adopted for the analysis of the MCEQ domain scores.

The following analyses will be conducted in only Group-2 PK analysis set:

- To test if the time to the maximum nicotine concentration in THS 2.2 is shorter than in NNS the following hypothesis will be evaluated:  
$$H_0: X_{THS} - X_{NNS} = 0 \quad H_A: X_{THS} - X_{NNS} < 0$$

Confidentiality Statement: Data and information contained in this document are considered to constitute trade secrets and confidential commercial information, and the legal protections provided to such trade secrets and confidential information are hereby claimed under the applicable provisions of applicable law. No part of this document may be publicly disclosed without the written consent of Philip Morris Products SA.

where  $X_{THS}$  and  $X_{NNS}$  are the median values of the THS 2.2 and NNS, respectively.  $t_{max}$  will be analysed on the original scale using the Wilcoxon Signed-Rank Test with a type I error  $\alpha = 0.025$  (one-sided test), as values are ordinal/discrete, and the assumption of normality may be questionable.

- To determine if the rate and the amount of nicotine absorbed of the THS 2.2 is higher relative to NNS the following hypothesis will be tested for both  $C_{max}$  and  $AUC_{(0-last)}$  parameters:

$$H_0: X_{THS}/X_{NNS} = 1.0 \quad H_A: X_{THS}/X_{NNS} > 1.0$$

where  $X_{THS}$  and  $X_{NNS}$  are the adjusted geometrical means of THS 2.2 and NNS, respectively.  $H_0$  is rejected with a type I error  $\alpha = 0.025$  (one-sided test), if the lower bound of the 95% CI for the  $X_{THS}/X_{NNS}$  ratio is higher than 1.0.

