#### 3.2 Secondary Objectives

The secondary objectives of this study are:

- To determine if  $C_{max}$  and  $AUC_{(0-last)}$  of the THS 2.2 are higher relative to NNS following single use of the THS 2.2 and NNS.
- To evaluate the difference on nicotine pharmacokinetic (PK) absorption parameters (AUC from start of product use extrapolated to time of last quantifiable concentration to infinity [ $AUC_{(0-\infty)}$ ] and partial AUC, where  $t'$  is the subject-specific time of maximum nicotine concentration following single use of the CC or NNS product [ $AUC_{(0-t')}$ ]) between the THS 2.2 and CC, as well as the THS 2.2 and NNS.
- To evaluate the time to the maximum concentration ( $t_{max}$ ) of nicotine for the THS 2.2 as compared to CC and to determine if the  $t_{max}$  for THS 2.2 is shorter as compared to NNS.
- To describe the terminal half-life ( $t_{1/2}$ ) of nicotine for the THS 2.2, CC, and NNS.
- To describe the differences on urge-to-smoke over time between the THS 2.2 and CC, as well as between the THS 2.2 and NNS.
- To describe product evaluation in the THS 2.2 and CC users.
- To describe the levels of carbon monoxide (CO) exposure for the THS 2.2, as compared to CC and NNS users.
- To monitor the safety during the study.

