Subjective effects of smoking: mixed effects ANOVA using period, sequence, and product exposure as fixed effects and subjects within sequence as random effects will be adopted to analyse the domain scores of the product evaluation (MCEQ) questionnaire, for the comparison between THS 2.2 and CC. The same model will be evaluated for the analysis of Urge-to-smoke (QSU-brief), including the assessment time points as repeated measurements. The results will be presented in terms of least square means and 95% CI for the THS 2.2-CC and THS 2.2-NNS differences.

**Safety:** The safety population will comprise all subjects, who are exposed to THS 2.2 during the study, including the THS 2.2 test at admission. Adverse event data will serve as the primary assessment of safety. All safety data will be listed and tabulated by sequence and by product use.

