### 3.2 Secondary Objectives

The secondary objectives of this study are:

- To determine if  $C_{max}$  and  $AUC_{(0-last)}$  of the THS 2.2 are higher relative to NNS following single use of the THS 2.2 and NNS.
- To evaluate the difference on nicotine pharmacokinetic (PK) absorption parameters (AUC from start of product use extrapolated to time of last quantifiable concentration to infinity [ $AUC_{(0-\infty)}$ ] and partial AUC, where  $t'$  is the subject-specific time of maximum nicotine concentration following single use of the CC or NNS product [ $AUC_{(0-t')}$ ]) between the THS 2.2 and CC, as well as the THS 2.2 and NNS.
- To evaluate the time to the maximum concentration ( $t_{max}$ ) of nicotine for the THS 2.2 as compared to CC and to determine if the  $t_{max}$  for THS 2.2 is shorter as compared to NNS.
- To describe the terminal half-life ( $t_{1/2}$ ) of nicotine for the THS 2.2, CC, and NNS.
- To describe the differences on urge-to-smoke over time between the THS 2.2 and CC, as well as between the THS 2.2 and NNS.
- To describe product evaluation in the THS 2.2 and CC users.
- To describe the levels of carbon monoxide (CO) exposure for the THS 2.2, as compared to CC and NNS users.
- To monitor the safety during the study.

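### The QSU-brief and COHb repeated-measures model has no time or product-by-time term, so it gives one product difference averaged over the day and no modelled difference over time

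*Protocol*

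**What the plan says.** The protocol's secondary objectives (section 3.2) include: "To describe the differences on urge-to-smoke over time between the THS 2.2 and CC, as well as between the THS 2.2 and NNS".

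For the analysis, section 12.6.3 takes over the terms of the mixed model that serves as the primary endpoints' sensitivity analysis and states that this model "will be adopted for the analysis of QSU-brief, including all of the different assessment time points as repeated measurements". The terms are listed in section 12.5.3: "Subjects within sequence will be used as random effects and fixed effects are period, sequence, and product exposure".

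Section 12.6.3 then says that there is no adjustment for the assessment before T0. It does not say whether that assessment is a response. For carbon monoxide: "Analysis of COHb levels will be conducted using a mixed model for repeated measures, the same approach as for the QSU-brief".

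The synopsis, both in the protocol and in its amended version, repeats the same fixed and random terms and announces the output: "The results will be presented in terms of least square means and 95% CI for the THS 2.2-CC and THS 2.2-NNS differences". It does not mention time points in the output.

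Section 12.6.3 also refers secondary endpoints to section 12.1.3, which plans descriptive statistics by exposure at each time point. Section 12.1 leaves full statistical detail to the SAP, which is not available here.

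**The concern.** The borrowed model was written for PK parameters, which give one value per subject per period, so it needs no time factor. QSU-brief gives ten values per single-use day and COHb gives five. Carrying the terms over unchanged forces the product difference to be the same at every assessment.

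A time main effect, if one is read into the repeated-measurements wording, does not solve this. In a balanced layout it removes the common time course but leaves the product contrast as the same average. Only a product-by-time interaction lets the difference vary with time.

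At stake is what the reported interval means. A single difference over a day on which the product is used once can be small because the products are alike, or because an early difference is averaged with assessments where none exists. The reader of the report could not tell which.

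**Working it through.** The protocol gives no effect size, sample size or power for QSU-brief or COHb, so there is no planned figure to reproduce. The check is a count of time points followed by the weighting that the stated model implies.

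**Inputs**
- QSU-brief (section 7.8.4): one assessment before T0, then 15, 30 and 45 min and 1, 2, 4, 6, 9 and 12 h. K = 10, of which 9 are post-use.
- COHb (section 7.5.1.1): one sample before T0, then 15 and 60 min and 4 and 12 h. K = 5, of which 4 are post-use.
- Fixed effects (section 12.5.3): period, sequence, product.

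**Formula.** Let d_k be the true product difference at time point k. In a balanced 2x2 crossover with no time terms, the product contrast estimates D = Σ w_k d_k, with the weights summing to 1. If the within-day covariance treats all time points alike, w_k = 1/K and D is the simple mean. Other covariance structures change the weights, but the result is still one weighted average.

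**Step 1: pre-use value as a response.** Let d_pre = 0 and let m be the mean post-use difference.
- QSU-brief: D = (0 + 9m)/10 = 0.90m, a 10% attenuation.
- COHb: D = (0 + 4m)/5 = 0.80m, a 20% attenuation.

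**Step 2: early and late times pooled.** The documents give no time course, so these profiles are assumptions. Each has a constant difference up to a cut-off and zero afterwards.

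| Difference lasts until | QSU-brief, all times | QSU-brief, post-use only | COHb, all times | COHb, post-use only |
|---|---|---|---|---|
| 60 min | 4/10 = 40% | 4/9 = 44% | 2/5 = 40% | 2/4 = 50% |
| 4 h | 6/10 = 60% | 6/9 = 67% | 3/5 = 60% | 3/4 = 75% |

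Entries are the pooled contrast as a share of the early difference. Under these profiles, dropping the pre-use value recovers only part of the loss; most of it comes from averaging early with late times.

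**Step 3: can the contrast distinguish time courses?** A difference of 1 at 15, 30 and 45 min only gives 3/10 = 0.3. A difference of 1 at 6, 9 and 12 h only also gives 3/10 = 0.3. Opposite time courses produce the same reported number.

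**Step 4: simulation check.** The settings were 40 subjects, 10 time points and 200 runs, with a true difference of 0.5 from 15 to 60 min and zero otherwise. The fit with period, sequence and product alone gave a mean pooled difference of 0.205, against 0.5 × 4/10 = 0.20 expected. Time-specific contrasts averaged 0.50 at 15-60 min, 0.01 later and 0.01 before use.

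**The case against.** The strongest reply is that the objective is to describe, and the protocol does describe: section 12.1.3 provides summaries by exposure at each time point. That stands. A reader might infer that the urge-over-time objective is not addressed at all; the documents do not support this. What is missing is narrower: a modelled, time-specific difference with a confidence interval. The carbon monoxide objective in section 3.2 concerns levels of exposure and does not ask for differences over time, so for COHb the point is attenuation and interpretability.

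A second reply is that the SAP may add the time terms. Section 12.1 does defer detail, but section 12.6.3 fixes the terms as those of the primary sensitivity model. An SAP with product-by-time would depart from a stated specification.

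Third, treating the pre-T0 value as a response is a literal reading of the word all. The next sentence of section 12.6.3 could suggest that it was thought of as a baseline. Also, the full section 12.6.3 is available only in the protocol before amendment. The supplied amended text ends in section 7.7, and its synopsis keeps the model terms but refers to the time points without that word. The 10% and 20% figures are therefore conditional; the missing interaction is not.

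Fourth, a reader might infer that ten values per day with only a subject random effect are counted as independent, so that the standard error is too small by a calculable factor. The documents do not support this. Entering time points as repeated measurements ordinarily implies a modelled within-subject covariance, whose structure is an SAP matter. An unmodelled time course would also inflate the residual and push the other way.

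Finally, a whole-day average is a legitimate summary. It does not, however, answer a question about time.

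**Conclusion.** The point holds in limited form. On the protocol's own wording, the QSU-brief model yields a single product difference averaged over time, while the objective is differences over time. COHb inherits the same structure.

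If the pre-use value is a response, time points have equal weight and there is no pre-use difference, the mean post-use difference is attenuated by 10% for QSU-brief and 20% for COHb. Pooling early and late assessments may dilute an early difference further. The 40% and 60% figures illustrate this for effects lasting 60 min and 4 h; they are not predictions. Applying the nicotine half-life from section 4.2 to craving to obtain one headline figure would go beyond the documents, which give no time course for urge.

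Severity is moderate. These are secondary endpoints; section 12.6.4 lists no confirmatory analysis and section 12.1.5 says that no claim rests on individual tests. The primary PK analysis and the sample size are unaffected.

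**What to change.** In section 12.6.3 and the synopsis, replace the reference to the primary sensitivity model's terms, for QSU-brief and COHb, with an explicit model:

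- **Responses:** post-T0 assessments only. State that the pre-T0 value is not a response in the product contrast and summarise it descriptively. The decision not to adjust for it can stay.
- **Fixed effects:** sequence, period, product, time and product-by-time.
- **Random effect and covariance:** subject within sequence, with the within-day covariance blocked on subject by period. The structure can be named in the SAP.
- **Output:** THS 2.2-CC and THS 2.2-NNS least squares mean differences with 95% CI at each post-T0 time point (nine for QSU-brief, four for COHb), plus one overall post-use average.

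The MCEQ model can keep its present terms, because that questionnaire is scheduled once per single-use day.

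The cost is protocol and SAP wording, more table rows, and wider intervals at single time points than for the average. No new data are needed. The change should be made before the analysis is run.
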